7.1. Adverse Events

Treatment-emergent adverse events (TEAEs) are defined as those AEs that develop or worsen after the first dose of double-blinded investigational product and up to 56 days beyond the last dose of investigational product. Analysis of AEs (as discussed below) will be limited to TEAEs, but data listings will include all AEs regardless of their timing.

All reported AEs will be coded using the current version of MedDRA and summarized by System Organ Class (SOC) and Preferred Term (PT). All summaries by SOC and PT will be ordered by decreasing frequency of participants within each SOC and then similarly by decreasing frequency of participants within each PT based on the pegcetacoplan group. In the case of equal frequency of number of participants in SOCs or PTs, summaries of TEAEs will be sorted alphabetically. Rules for handling missing severity, relationship to study drug, relationship to infusion procedure, outcome, and missing dates of AEs are described in Section 13.

If a PT was reported more than once for the same participant, that participant would only be counted once in the incidence for that PT. For participants experiencing the same PT at multiple severities, the occurrence of the AEs with the greatest severity will be used in the analysis of incidence by severity. For participants experiencing the same PT at multiple relationship levels, the occurrence of the AEs with the strongest relationship to study drug will be used in the analysis of incidence by relationship to study drug.

The AE summaries will be presented by treatment group. In addition, the incidence of death, stratified by transplant history will be summarized.

In post-transplant participants, the number and incidence of rejection episodes at week 26 will be tabulated by treatment group. Additionally, if the number of participants is sufficient, the results for treatment groups will be compared using Fisher's exact test (or a stratified Cochran-Mantel-Haenszel χ -square test as appropriate).

In participants who are posttransplant, the number and incidence of graft loss at week 26 will be tabulated by treatment group. Additionally, if the number of participants is sufficient, the results for treatment groups will be compared using Fisher's exact test (or a stratified Cochran-Mantel-Haenszel γ -square test as appropriate).

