An overall summary for TEAEs, including number of participants who experience a TEAE, number of total TEAEs, and number of unique TEAEs, will be provided:

- TEAE
- Treatment-related TEAE
- Infusion-related TEAEs
- Serious TEAE
- Maximum severity of TEAEs
- Infusion site reaction
- TEAE leading to treatment withdrawn
- TEAE leading to dose interruption
- TEAE leading to study discontinuation
- TEAE leading to death
- Rejection episodes (for posttransplant only, based on PTs of "KIDNEY TRANSPLANT REJECTION", "RENAL AND PANCREAS TRANSPLANT REJECTION", "MULTIPLE ORGAN TRANSPLANT REJECTION", "SOLID ORGAN TRANSPLANT REJECTION")
- Graft loss (for posttransplant only, based on PTs of "TRANSPLANT FAILURE",
 "ENGRAFT FAILURE", "RENAL TRANSPLANT FAILURE", "REMOVAL OF
 RENAL TRANSPLANT", "GRAFT LOSS")

The following summaries will be provided:

- TEAEs by SOC and PT
- TEAEs by PT in decreasing order of frequency
- Treatment-related TEAEs by SOC and PT
- Infusion-related TEAEs by SOC and PT
- Serious TEAEs by SOC and PT
- TEAE by SOC, PT and maximum severity
- TEAE leading to treatment discontinuation by SOC and PT
- TEAE leading to dose interruption by SOC and PT
- TEAE leading to study discontinuation by SOC and PT
- TEAE leading to death by SOC and PT
- Treatment-emergent adverse events of special interest (AESIs) by SOC and PT
- Serious treatment-emergent AESIs by SOC and PT
- Exposure-adjusted incidence TEAEs by SOC and PT
- Exposure-adjusted incidence serious TEAEs by SOC and PT

Exposure-adjusted incidence rate of an AE is defined as the number of events divided by the total duration of exposure of the participants at risk during treatment, which is computed as following:

Exposure-adjusted incidence rate = n*100/EY,

where n is the number of participants impacted; the exposure year (EY) = (sum of time to onset of the event)/365.25, where time to onset of the event = date of onset of event – Day 1 date +1. For participants without the event, time to onset is censored as follows: time to onset of the event = (last dose date + 56 days) – Day 1 date +1. For participants who experienced the same event on multiple occasions: time to onset of the event = date of onset at the first occasion – Day 1 date +1.

The following listings will be provided:

- All AEs
- Serious adverse events (SAEs)
- AEs leading to study drug discontinuation
- Death
- Treatment-related adverse events
- Infusion-related adverse events

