1. INTRODUCTION

This statistical analysis plan (SAP) addendum provides a technical and detailed elaboration of the statistical analyses of efficacy and safety, supplementing what is described in the main SAP of the primary analysis (Week 26) and overall (combined with Week 26 SAP) clinical study report (CSR). The specified analyses to be performed as part of this SAP addendum do not supersede or replace any previously specified analyses, unless specified otherwise.

The specified analyses in this SAP addendum will serve the purposes of the planned analyses for the open-label period (OLP) reporting once all participants have completed the open-label treatment period or discontinued early and all corresponding data have been entered into the database, reviewed, cleaned, and finalized, and the database is locked.

The analyses of the OLP data associated with the primary CSR (dated 05 December 2024) were described in Version 1.0 of the SAP Addendum.

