6.7.16. Time to 50% Reduction in uPCR with a Stable or Improved eGFR

The analysis described in Section 6.7.6 in the main SAP will be repeated based on the ITT set using all available data through the Week 52 assessment. For event-free survival, present the timepoints of week 12, week 24, week 36, and week 48.

6.7.17. Time to Normalization for Selected Parameters for Participants in Whom the Parameter is Abnormal at Baseline

The analysis described in Section 6.7.7 in the main SAP will be repeated based on the ITT set using all available data through the Week 52 assessment. For event-free survival, present the timepoints of week 12, week 24, week 36, and week 48.

Note for time to normalization of serum C3, the normalization is not applicable for this endpoint hence the analysis is revised as time to serum C3 levels being greater than or equal to the lower limit of normal (LLN). This also applies to the analysis for the RCP period.

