7. SAFETY ANALYSIS

7.1. Adverse Events

Further detail is provided in the main SAP Section 7.1. The same summaries for RCP as in the main SAP will be repeated for OLP (except for rejection episodes and graft loss where only descriptive summaries are required at Week 52) using all available data through the Week 52 assessment.

Besides the AESI summaries as per the CRF form checkbox question "Is this event an AESI?", additional summaries for the AEs of special search will be provided based on the special search teams provided by Apellis safety team, more specifically:

- Infections: SOC-infections and infestations; HLGT- Bacterial infectious disorders, HLGT- Fungal infectious disorders, HLGT- Viral infectious disorders
- Hypersensitivity: SMQ-Hypersensitivity (narrow)
- Acute Kidney Injury: SMQ- Acute Renal Failure (narrow)
- Thrombocytopenia: HLT- Thrombocytopenias, PT-Platelet count decreased, PT-Plateletcrit decreased, PT-Platelet count abnormal

AEs will be summarized by treatment groups and period. Data will be presented in 5 columns: (1) Pegcetacoplan group's RCP results; (2) Pegcetacoplan group's OLP results; (3) Placebo group's OLP results; (4) OLP results combined (in other words, combining columns 2 and 3); (5) for all results since Pegcetacoplan injection (in other words, combining columns 1 and 4). The classification of AEs in the RCP or OLP will be based on the AE start date compared to the RCP/OLP threshold as defined in the main SAP Section 13.3.

For AE summaries that relate to rejection episodes, in addition to the preferred terms specified in the main SAP, one additional preferred term of "Transplant rejection" is also added based on Apellis team review.

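### The SAP Addendum widens the rejection-episode definition from four preferred terms to five without saying whether the week 26 randomized-period analysis follows, so one safety endpoint can carry two definitions across the two reports.

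*SAP*

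**What the plan says.** The number and incidence of rejection episodes in posttransplant participants is a protocol safety endpoint (Protocol Section 5.2.2). Protocol Section 12.4 plans a between-arm comparison at week 26 and tabulation only at week 52.

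Main SAP Section 7.1 implements this for the RCP: "the number and incidence of rejection episodes at week 26 will be tabulated by treatment group". A Fisher or Cochran-Mantel-Haenszel test is added if there are enough participants. The event is defined by a list: "Rejection episodes (for posttransplant only, based on PTs of" four terms, which name rejection of a kidney, of kidney and pancreas together, of multiple organs and of a solid organ. The unspecific term *Transplant rejection* is not among them.

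SAP Addendum version 2.0, Section 7.1, changes the list: "in addition to the preferred terms specified in the main SAP, one additional preferred term of" *Transplant rejection* is added, on the basis of a review by the sponsor's team. The same section sets the column layout for adverse-event tables: "1) Pegcetacoplan group's RCP results; (2) Pegcetacoplan group's OLP results; (3) Placebo group's OLP results", then the two open-label (OLP) columns combined, and a fifth column "for all results since Pegcetacoplan injection (in other words, combining columns 1 and 4".

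Two further places bear on scope. Addendum Section 1 says that its analyses "do not supersede or replace any previously specified analyses, unless specified otherwise". Where the addendum wants a change carried back, it says so. "This also applies to the analysis for the RCP period" stands in Section 6.7.17 on serum C3, and the same statement is made for the changes in Sections 6.7.1, 6.7.19, 6.7.20, 8 and 9. It is absent from the rejection change in Section 7.1 and from the list of changes in Section 15.

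**The concern.** A safety endpoint should be counted in the same way wherever it is reported. Here the count depends on the report. An RCP event coded only as *Transplant rejection* would be left out of the week 26 rejection row in either arm. In the pegcetacoplan arm, the same event would be counted in addendum columns 1 and 5. In the placebo arm, no specified table would count it as a rejection episode.

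A reader of the final report who wants a control figure for the pegcetacoplan rejection counts has only the week 26 placebo count, which uses the shorter list. The posttransplant subgroup is small, so a single event is visible in the percentages.

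Timing adds to the need for a clear label. According to Addendum Section 11, the RCP results were reported in a study report dated 05 December 2024. The addendum that makes the change is dated 10 February 2025.

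**Working it through.** The plan gives no figure to reproduce on this point. The check sets the term lists side by side and then sizes the effect of one event.

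**Step 1: which list governs each arm and period**

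| Arm and period | Main SAP 7.1 | Addendum 7.1 |
|---|---|---|
| Pegcetacoplan, RCP | 4 terms | 5 terms (columns 1, 5) |
| Placebo, RCP | 4 terms | no column |
| Pegcetacoplan group, OLP | outside its scope | 5 terms (columns 2, 4, 5) |
| Placebo group, OLP (on pegcetacoplan) | outside its scope | 5 terms (columns 3, 4, 5) |

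Three results follow.

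- The randomized comparison uses the first two cells of the main SAP column: four terms against four.
- Pegcetacoplan RCP is the only cell with two lists, so it can have two counts.
- Placebo RCP is the only cell never counted on five terms. It is also the only placebo-treated time in the trial.

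**Step 2: direction.** Adding a term can only leave a count unchanged or raise it. All five addendum columns hold time on pegcetacoplan. If they are read against the week 26 placebo count, any mismatch therefore adds events to pegcetacoplan only.

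**Step 3: size of one event.** Protocol Section 6.2 allows up to 22 posttransplant participants, so 1:1 randomization gives about 22/2 = 11 per arm. The actual number is not in the documents; smaller values are assumptions. One extra participant with an event changes an arm's incidence by 100/n percentage points:

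- n = 11: 100/11 = 9.1
- n = 8: 100/8 = 12.5
- n = 5: 100/5 = 20.0
- n = 3: 100/3 = 33.3

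**Step 4: effect on the between-arm test.** With k events among n participants in one arm, none among n in the other and k no larger than n, the two-sided Fisher p-value is 2 × C(n,k)/C(2n,k). At n = 11:

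- k = 1: 2 × 11/22 = 1.0
- k = 2: 2 × 55/231 = 0.476
- k = 3: 2 × 165/1540 = 0.214
- k = 4: 2 × 330/7315 = 0.090
- k = 5: 2 × 462/26334 = 0.035

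Against zero events, five are needed to fall below 0.05. One recoded event is very unlikely to change the test's conclusion. What can change is the reported incidence.

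**The case against.** The strongest reply is that nothing is wrong with the randomized comparison. A reader might infer that placebo is counted on the narrow list and pegcetacoplan on the wide one within that comparison. The documents do not support this: main SAP Section 7.1 applies the same four terms to both arms. The mismatch appears only across reports, and no section plans that cross-reading. Addendum Section 7.1 asks only for descriptive rejection summaries at week 52. This objection stands and limits the point.

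Several further replies also hold.

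- A reader might infer that the added term is restricted to the addendum's own tables. The addendum never says so; its wording covers adverse-event summaries of rejection without naming a period, and column 1 is RCP data. The restriction is an inference from the Section 1 rule, the missing carry-back statement and the missing placebo RCP column. It is a strong inference, but what can be shown is an unstated scope.
- A reader might infer that events were missed. Nothing shows that any event in either arm was coded to the term. The addendum attributes the addition to team review, which could have been a precaution or prompted by an OLP event.
- Such an event would not vanish. Main SAP Section 7.1 also requires treatment-emergent events by preferred term and a listing of all adverse events. Only the derived rejection row could omit it.
- The change is disclosed in the addendum's revision history and in its Section 15, and its direction works against the sponsor's drug.

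None of this removes the need for one stated definition. If the sponsor meant the term to cover all periods, the missing statement is the defect. If not, pegcetacoplan RCP has two lists by design.

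**Conclusion.** The point holds as a minor inconsistency. The rejection definition grew from four terms to five after the RCP results were reported, and the addendum does not say whether the RCP analysis follows. As written, pegcetacoplan RCP rejections can differ between the two reports. Addendum columns 1 and 5 also cannot be compared with the week 26 placebo count.

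The documents support no claim of bias in favour of pegcetacoplan, of unequal definitions within the week 26 comparison, or of any event actually lost. The size is conditional: if one RCP event carries only the added term, an arm's incidence moves by 9.1 percentage points at 11 per arm and by 33.3 at an assumed 3 per arm. If no event carries it, nothing changes. The conclusion assumes that main SAP analyses stand unless the addendum says otherwise, which is the addendum's own rule.

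**What to change.** State in Addendum Section 7.1 that the five-term list also applies to the RCP. Keep the prespecified four-term week 26 result. Beside it, tabulate week 26 rejection episodes for both arms on five terms, with the between-arm test only if numbers are sufficient. Label that table as a post hoc change made after the RCP results were reported. If no RCP event carries the added term, replace the table with a footnote that says so.

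The cost is one sentence plus one table or footnote, added after a study report that is already complete.

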7.2. Clinical Laboratory Data

Refer to main SAP Section 7.2 for further details of the analysis.

The same by-visit summaries as in the main SAP will be repeated using all available data through the Week 52 assessment.

7.3. Vital Signs

Refer to main SAP Section 7.3 for further details of the analysis.

The same by-visit summaries as in the main SAP will be repeated using all available data through the Week 52 assessment.

7.4. Electrocardiogram (ECG)

Refer to main SAP Section 7.4 for further details of the analysis.

The same by-visit summaries as in the main SAP will be repeated using all available data through the Week 52 assessment.

7.5. Other Safety Data

Physical examinations will be described in a data listing using all available data through the Week 52 assessment.

8. PHARMACOKINETIC ANALYSIS

Refer to main SAP Section 8 for further details of the analysis.

The same summaries for RCP as in the main SAP will be repeated using all available data through the Week 52 assessment.

Note the individual linear and loglinear PK plots will be removed from planned analysis, given the relevant data listings already provided sufficient information. This also applies to the analysis for the RCP period.

9. PHARMACODYNAMIC ANALYSIS

Refer to main SAP Section 9 for further details of the analysis.

The same summaries for RCP as in the main SAP will be repeated using all available data through the Week 52 assessment.

Note the individual PD and change from baseline PD plots will be removed from planned analysis, given the relevant data listings already provided sufficient information. This also applies to the analysis for the RCP period.

10. IMMUNOGENICITY

Refer to main SAP Section 10 for further details of the analysis.

The same summaries for RCP as in the main SAP will be repeated using all available data through the Week 52 assessment.

11. INTERIM ANALYSIS

An analysis was conducted for regulatory submissions when all participants have completed the randomized controlled period and the data was cleaned. No type I error adjustment was necessary. Results were reported in the CSR (dated 05 December 2024).

12. DATA MONITORING COMMITTEE

Refer to main SAP Section 12 for more details.

13. DATA HANDLING CONVENTIONS

Refer to main SAP Section 13 for more details.

In addition, for analysis based on OLP set, baseline is defined as the most recent non-missing measurement prior to the start of open-label period for both pegcetacoplan group and placebo group, with the exception of triplicate FMU uPCR, where an average of up to 9 collections from Week 24, 25, and 26 will be used for baseline derivation when applicable.

14. ANALYSIS SOFTWARE

Refer to main SAP Section 14 for more details.

15. CHANGES TO ANALYSIS SPECIFIED IN PROTOCOL

Changes in this SAP Addendum that were not described in the protocol or main SAP are:

- Added shift table summary of FMU uPCR by categories.
- Removed biopsy-related analysis at Week 52 given the Week 52 biopsy being optional.
- Revised slope analysis at Week 52 for primary endpoint and key secondary endpoint of eGFR.
- Revised 24-hour uPCR modeling by using log-transformed uPCR values.
- Revised analysis for time to normalization of serum C3.
- Revised analysis for PGIC score and EQ-5D-5L score.
- Added more details on AEs of special search summaries and rejection episode definition.
- Removed individual plots for PK and PD analysis due to redundancy.

17. APPENDICES

Refer to main SAP Section 17 for more details.
